7.9.1.2. Adverse Events of Special Interest

The Investigator will monitor each patient for clinical and laboratory evidence for pre-defined AEs of special interest (AESIs) through LFU.

For this study, GI intolerance and anemia are considered AESIs. During the course of the study, additional AESIs may be identified by the Sponsor.

Examples of AESIs related to GI intolerance include, but are not limited to: *C. difficile* colitis, Pseudomembranous colitis, *C. difficile* test positive, diarrhea, nausea, and vomiting.

Examples of AESIs related to anemia include, but are not limited to: anemia, aplastic anemia, Coombs negative hemolytic anemia, Coombs positive hemolytic anemia, hematocrit decreased, hemoglobin decreased, hemolysis, hemolytic anemia, intravascular hemolysis, and RBC decreased.

7.9.2. Serious Adverse Events

An AE or adverse reaction is considered serious if, in the view of either the Investigator or Sponsor, it results in any of the following outcomes:

- Death
- A life-threatening AE

Note: An AE or adverse reaction is considered “life-threatening” if, in view of either the Investigator or Sponsor, its occurrence places the patient at immediate risk of death. It does not include an event that, had it occurred in a more severe form, might have caused death.

- Requires hospitalization or prolongation of existing hospitalizations

Note: Any hospital admission with at least 1 overnight stay will be considered an inpatient hospitalization. An emergency room or urgent care visit without hospital admission will not be recorded as a SAE under this criterion, nor will hospitalization for a procedure scheduled or planned before signing of informed consent, or elective treatment of a preexisting condition that did not worsen from baseline. However, unexpected complications and/or prolongation of hospitalization that occur during elective surgery should be recorded as AEs and assessed for seriousness. Admission to the hospital for social or situational reasons (ie, no place to stay, live too far away to come for hospital visits, respite care) will not be considered inpatient hospitalizations.

- A persistent or significant disability/incapacity or substantial disruption of the ability to conduct normal life functions
- A congenital anomaly/birth defect

Important medical events that do not meet any of the above criteria may be considered an SAE when, based upon appropriate medical judgment, they may jeopardize the patient and may require medical or surgical intervention to prevent one of the outcomes listed above. Examples of such medical events include allergic bronchospasm requiring intensive treatment in an emergency room or at home, blood dyscrasias or convulsions that do not result in inpatient hospitalizations, or the development of drug dependency.

Events of progression of a patient’s underlying disease including worsening signs/symptoms associated with the underlying MAC lung infection should not be reported as an SAE unless the outcome is fatal or requires hospitalization during the study or within the safety reporting period. If the event has a fatal outcome during that timeframe, the event must be recorded as an SAE with CTCAE Grade 5 (fatal) outcome indicated. Diagnosis of progression of disease alone should not be reported as an SAE.

SAEs will be reviewed by the Sponsor Medical Monitor and/or safety physician and further queries issued, if necessary. The ultimate determination of causality will be made in consideration of ICH and FDA guidelines.

7.9.3. Serious Adverse Event Reporting – Procedures for Investigators

7.9.3.1. Initial reports

All SAEs occurring from the time of informed consent through LFU must be reported to [REDACTED] Clinical Safety without undue delay but no later than within 24 hours of the knowledge of the occurrence. After LFU, any SAE that the Investigator considers related to study drug must be reported to the [REDACTED] Clinical Safety or the Sponsor/designee.

To report the SAE, complete the SAE form electronically in the EDC system for the study. When the form is completed, Medpace Safety personnel will be notified electronically by the EDC system and will retrieve the form. If the event meets serious criteria and it is not possible to access the EDC system, send an email to [REDACTED] Safety at [REDACTED] or call the [REDACTED] SAE reporting line (phone number listed below), and fax/email the completed paper SAE form to [REDACTED] (contact information listed in [Section 7.9.6](#)) within 24 hours of awareness. When the EDC system becomes available, the SAE information must be entered within 24 hours of the system becoming available.

7.9.3.2. Follow-up Reports

The Investigator must continue to follow the patient until the SAE has subsided or until the condition becomes chronic in nature, stabilizes (in the case of persistent impairment), or the patient dies.

Within 24 hours of receipt of follow-up information, the Investigator must update the SAE form electronically in the EDC system for the study and submit any supporting documentation (eg, patient discharge summary or autopsy reports) to [REDACTED] Clinical Safety via fax or e-mail. If it is not possible to access the EDC system, refer to the procedures outlined above for initial reporting of SAEs.

7.9.4. Pregnancy Reporting

If a patient becomes pregnant during the study or within the safety follow-up period defined in the Protocol, the Investigator is to stop dosing with study drug(s) immediately and the patient should be withdrawn from the study. Early termination procedures should be implemented at that time.

A pregnancy is not considered to be an AE or SAE; however, it must be reported to [REDACTED] Clinical Safety within 24 hours of knowledge of the event. [REDACTED] Clinical Safety will then provide the Investigator/site the Exposure In Utero (EIU) form for completion. The Investigator/site must complete the EIU form and fax/email it back to [REDACTED] Clinical Safety.

If the female partner of a male patient becomes pregnant while the patient is receiving study drug or within the safety follow-up period defined in the Protocol, the Investigator should notify

████████ Clinical Safety as described above. The Investigator/site must make every effort to obtain a completed informed consent form (ICF) for the pregnant partner of a male patient.

The pregnancy should be followed until the outcome of the pregnancy, whenever possible. Once the outcome of the pregnancy is known, the EIU form should be completed and faxed/emailed to

████████ Clinical Safety. If the outcome of the pregnancy meets the criteria for immediate classification as an SAE (ie, postpartum complication, spontaneous abortion, stillbirth, neonatal death, or congenital anomaly), the Investigator should follow the procedures for reporting an SAE.

7.9.5. Expedited Reporting

The Sponsor/designee will report all relevant information about Suspected Unexpected Serious Adverse Reactions (SUSARs) that are fatal or life-threatening as soon as possible to the FDA, applicable competent authorities in all the countries and Member States concerned, and to the IECs, and in any case no later than 7 days after knowledge by the Sponsor/designee of such a case. Relevant follow-up information will subsequently be communicated within an additional 8 days.

All other SUSARs will be reported to the FDA, applicable competent authorities concerned, and to the IECs concerned as soon as possible but within a maximum of 15 days of first knowledge by the Sponsor/designee.

The Sponsor/designee will also report any additional expedited safety reports required in accordance with the timelines outlined in country-specific legislation.

The Sponsor/designee will also inform all Investigators as required per local regulation.

The requirements above refer to the requirements relating to IMP.

Expedited reporting of SUSARs related to non-investigational medicinal products (NIMPs) (and any other NIMPs) is not required. Listings of cases related to NIMPs will be included in the Development Safety Update Report.

7.9.6. Special Situation Reports

Special situation reports include reports of overdose, misuse, abuse, medication error, and reports of adverse reactions associated with product complaints.

- **Overdose:** Refers to the administration of a quantity of a medicinal product given per administration or cumulatively (accidentally or intentionally), which is above the maximum recommended dose according to the Protocol. Clinical judgment should always be applied. In cases of a discrepancy in the drug accountability, overdose will be established only when it is clear that the patient has taken additional dose(s) or the Investigator has reason to suspect that the patient has taken additional dose(s).
- **Misuse:** Refers to situations where the medicinal product is intentionally and inappropriately used in a way that is not in accordance with the Protocol instructions or local prescribing information and may be accompanied by harmful physical and/or psychological effects.

- Abuse: Is defined as persistent or sporadic, intentional excessive use of a medicinal product, which is accompanied by harmful physical or psychological effects.
- Medication error: Is any unintentional error in the prescribing, dispensing, or administration of a medicinal product by a healthcare professional, patient, or consumer, respectively. The administration or consumption of the unassigned treatment and administration of an expired product are always reportable as medication errors, cases of patients missing doses of study drug are not considered reportable as medication error.
- Product complaint: Is defined as any written, electronic, or oral communication that alleges deficiencies related to the identity, quality, durability, reliability, safety, effectiveness, or performance of a drug or device after it is released for distribution. A special situations form will only be completed if a complaint is associated with an adverse drug reaction.

All special situation events as described above must be reported on the Special Situations Report form and faxed/emailed to [REDACTED] Clinical Safety (contact information listed below) within 24 hours of knowledge of the event. All AEs associated with these Special Situation reports should be reported as AEs or SAEs as well as recorded in the AE eCRF and/or the SAE report form. Details of the symptoms and signs, clinical management, and outcome should be provided, when available.

Safety Contact Information: [REDACTED] Clinical Safety

8. STATISTICS

8.1. Analysis Populations

The following analysis populations will be defined in this study:

- Intent-to-Treat (ITT) Population: All patients who were randomized, regardless of whether they received any study drug
- Safety Population: Randomized patients who received any amount of study drug
- Micro-ITT Population: Patients who meet the definition for the ITT Population and have MAC culture-positive *Pre-Study* and *Screening* respiratory specimens (per Inclusion Criterion 3.a). Primary efficacy endpoint analyses in both Phase 2 and Phase 3 parts of the study will be performed in this patient population.
- Per-Protocol Population: Patients who meet the definition for the ITT Population and have no important protocol deviations that would affect the assessment of the primary efficacy outcome
- PK Population: All patients treated with at least 1 dose of epetraborole and who have at least 1 analyzable PK sample
- Full Analysis Set-PRO (FAS-PRO) (applicable to Phase 2 part only): The psychometric analyses will be conducted using blinded data from the FAS-PRO, and all available data will be included. The Full Analysis Set is identical to the ITT Population. The FAS-PRO will include all randomized patients who have MACrO₂ PRO data at Screening and Day 1 (for test-retest reliability assessment), Day 1, and at least Month 3 and/or Month 6 (for all other calculations).
- Embedded Interview Population (applicable to Phase 2 part only): Up to 40 Phase 2 patients who meet Micro-ITT Population and interview eligibility (per [Section 7.5.6](#))

8.2. Statistical Methods

8.2.1. Analysis of Efficacy

Different primary and key secondary endpoints will be used for the purposes of review in the US and outside of the US, and full details of these analyses will be outlined in the SAP(s). The primary analysis population for the US and outside of the US will be the Micro-ITT Population.

Additional sensitivity analyses to address the impact of missing data due to COVID-19 may be added to the SAP.

8.2.1.1. Phase 2 Part of the Study

The Phase 2 part of the study will assess the performance of the MACrO₂ PRO, including responsiveness to change, with the aim of informing selection of the optimal PRO to be used in the Phase 3 part of the study. Psychometric analyses will aim to identify the most appropriate threshold to use within the target population for the individual MACrO₂ PRO items. This process will be outlined in the psychometric analysis plan. In summary, anchor-based approaches will be used to assess and confirm the proposed definition of clinical response (ie, improvement of

≥ 1 grade in the key symptom with no worsening of other symptoms for the MACrO₂ PRO). Empirical cumulative distribution function and probability density plots will also be examined. Distribution-based analyses will be used as supplemental evidence ([FDA, 2019](#)). Anchors will include other PRO measures (ie, the PGIS and PGIC) or clinical outcomes such as microbiological response. The results will be triangulated with the anchor-based analyses considered to be the primary evidence, distribution-based analyses treated as secondary evidence, and results from the embedded interviews to determine a single responder definition threshold or narrow ranges of values for the MACrO₂ PRO items.

In addition to the evaluation of the PROs, endpoints from the Phase 2 part of the study will undergo statistical analyses to estimate the effect of randomized treatment. The number and percentage of PRO symptom/function-based clinical responders and clinical non-responders will be presented by treatment group, as will the percentage of patients achieving a microbiological improvement or a microbiological sputum culture conversion. In each case, the response rate will be compared between treatment groups using the method of Miettinen and Nurminen. Statistical analysis of all endpoints for the Phase 2 part of the study will be described in the SAP(s).

After the last patient in Phase 2 completes the Month 6+1 week PRO assessment, prespecified members of the Sponsor and non-Sponsor analysis teams will be unblinded to treatment assignment for Phase 2 data analyses, but study staff conducting psychometric validation analyses will remain blinded. Patients, Investigators, and other study staff will also remain blinded to treatment assignment through LFU (see Study Blinding Plan). Prespecified members of the Sponsor and non-Sponsor analysis teams will review unblinded results from the Phase 2 analyses, based on data through Month 6, to verify the appropriate PRO measure and clinical response determinations for the superiority analysis in the Phase 3 part of the study. The current symptom-based clinical response definition (using the MACrO₂ PRO) in Phase 3 is a placeholder to be verified after Phase 2 analyses. Potential changes to clinical response criteria in the Phase 3 part of the study will be programmatic in nature and will not affect study conduct; regardless of the PRO or clinical responses determined for the Phase 3 primary analysis, patients in both the Phase 2 and Phase 3 parts of the study will complete the same set of PRO measures and microbiological assessments according to the Schedule of Assessments ([Appendix A](#)).

8.2.1.2. Phase 3 Part of the Study

The number and percentage of PRO symptom/function-based clinical responders and clinical non-responders will be presented by treatment group. Patients with missing data or incomplete PRO data at each relevant time point will be considered an indeterminate response and will be analyzed as a clinical non-responder. The clinical response rate will be compared between treatment groups using the method of Miettinen and Nurminen. Analyses of PRO symptom/function-based clinical responses will be conducted in the Micro-ITT and Per-Protocol populations.

The number and percentage of patients with microbiological responses by both decrease in MAC colony counts of ≥ 1 category and sputum culture conversion will be presented by treatment group. Microbiological responses will be compared between treatment groups using the method of Miettinen and Nurminen. Analyses of microbiological responses will be conducted in the Micro-ITT Population.

As there is 1 primary endpoint and 1 key secondary endpoint in each region (in the US or outside the US), a hierarchical testing approach will be applied, whereby the primary endpoint will be tested, and if superiority is concluded for the primary endpoint, the key secondary endpoint will then be tested. Note that, although the ordering of the primary endpoint and key secondary endpoint is reversed for the US and outside the US, the same approach to hierarchical testing will be used for the primary and key secondary endpoint appropriate for that region. As no specific claims are intended for other secondary endpoints, no further multiplicity testing will be applied for the other secondary and exploratory endpoints.

Analyses of the exploratory efficacy outcomes will be conducted to support the findings of the primary and secondary efficacy outcomes and will be described in the SAP(s).

8.2.2. Analysis of Safety

Safety will be evaluated for the Safety Population by presenting the summaries of TEAEs, clinical laboratory evaluations (chemistry, hematology, and urinalysis), vital signs, and 12-lead ECG parameters. A TEAE is defined as an AE that occurs during or after the first administration of study drug on Day 1 through the EOT Visit. All SAEs occurring from the time of informed consent through LFU will be collected.

AEs will be coded using the Medical Dictionary for Regulatory Activities (MedDRA) v25.0 or later. An overall summary of AEs will be provided by treatment group. The incidence of TEAEs will be presented by SOC and PT; by SOC, PT, and relationship to study drug; and by SOC, PT, and maximum severity. SAEs and TEAEs that lead to premature discontinuation of study drug will also be presented by SOC and PT.

Descriptive statistics for clinical laboratory results, vital signs, and 12-lead ECG parameters, including change from baseline, will be presented by time point collected. Incidences of potentially clinically significant clinical laboratory results, vital signs, and 12-lead ECG parameters, as defined in the SAP(s), will also be summarized.

8.2.3. Analysis of Pharmacokinetics

Plasma PK will be analyzed for all patients treated with at least 1 dose of epetraborole and who have at least 1 analyzable PK sample. A population PK analysis will be performed to assess exposure and PK parameters of epetraborole. Plasma PK samples obtained from the epetraborole group will be analyzed using a validated assay by a central bioanalytical laboratory. Samples from placebo-treated patients will not be analyzed. Masked individual and composite plasma PK data from an initial group of patients in the Phase 2 part of the study will be reviewed by a PK Data Review Committee to assess epetraborole exposures ([Section 8.3.1](#)). Approximately 40 of the initial patients enrolled may need to be considered in this evaluation to ensure approximately 16 epetraborole-treated patients from the PK Population contribute to the exposure confirmation. The methods to be employed for this interim analysis will be presented in a data analysis plan and results reported in a separate PK report.

8.2.4. Sample Size Determination

8.2.4.1. Phase 2 Part of the Study

The Phase 2 sample size ($n=80$) is based on the planned psychometric evaluation of the MACrO₂ PRO and is a sample size which may indicate an initial efficacy signal from this part of the study. When evaluating the individual items of the MACrO₂ PRO (not a scale with a total score), analyses will be within-patient, and this blinded evaluation will include patients from both treatment groups. As a result, sample size requirements are not as high as in studies evaluating measures with composite scores. Basing assumptions on convergent correlations with 90% power, an alpha of 0.05, and expected correlation coefficient of 0.4, the minimum sample size needed is 61; therefore, a total Phase 2 sample size of 80 patients will be appropriate (polychoric correlations will be assessed given the MACrO₂ PRO uses rating scales with 5 response options). In addition, using assumed true response rates of 30% for the epetraborole arm and 10% for the placebo arm for either a PRO symptom-based clinical response (in the US) or a microbiological culture conversion response (outside the US), a Phase 2 evaluation in 40 patients per arm would have 85% power to show a significant treatment effect using a 2-sided alpha of 0.2. Therefore, this sample size is considered sufficient to provide the potential to show a preliminary efficacy signal.

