3.1.2. Number of Patients

A total of approximately 314 patients will be enrolled in this Phase 2/3 study:

- The Phase 2 part of the study will consist of approximately 80 randomized patients (40 patients in the epetraborole + OBR group and 40 patients in the placebo + OBR group).
- The Phase 3 part of the study will consist of approximately 234 randomized patients (156 patients in the epetraborole + OBR group and 78 patients in the placebo + OBR group). The number of patients in the Phase 3 part of the study may be adjusted based on the results of Phase 2 analyses.

See [Section 8.2.4](#) for further details.

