8.2.4.2. Phase 3 Part of the Study

No data are available on clinical symptom response or minimal clinically important differences (MCIDs) using available PROs in patients with treatment-refractory MAC lung disease; therefore, previously published Month 6 sputum culture conversion rates in treatment-refractory MAC lung disease were used to initially estimate the number of patients expected to have an MCID improvement in PRO score, assuming a correlation between microbiological response and clinical symptom improvement. A Phase 3 study comparing ALIS + OBR versus OBR alone in patients with treatment-refractory MAC lung disease revealed Month 6 sputum culture conversion rates of 29.0% compared with 8.9%, respectively ([Griffith, 2018](#)). Therefore, the initial sample size estimate for the Phase 3 part of the study assumes that the true number of patients experiencing an MCID improvement in PRO score is 30% for the epetraborole + OBR arm and 10% for the placebo + OBR arm. Assuming a 2:1 randomization and a 2-sided alpha of 0.05, a Phase 3 study of 186 patients with proven MAC lung disease in the primary analysis (124 patients in the epetraborole + OBR arm and 62 patients in the placebo + OBR arm) would provide approximately 90% power, while also assuming an analysis of proportions using the method of Miettinen and Nurminen. The total sample size for the Phase 3 part of the study is estimated to be 234 patients (156 epetraborole and 78 placebo patients) rather than 186 patients, to allow for approximately 20% of randomized patients to be excluded from the Micro-ITT Population due to lack of a study qualifying baseline culture ([Griffith, 2018](#)) (see Inclusion Criterion [3.a](#)); therefore, 186 patients are expected to be included in the Micro-ITT Population for the primary efficacy analysis. The sample size for Phase 3 will be reassessed after Phase 2 analyses, which will be based on data through Month 6. Any needed sample size adjustment for Phase 3 will be determined as part of the review of unblinded Phase 2 data.

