1 INTRODUCTION

This Statistical Analysis Plan (SAP) provides a description of the statistical methods to be implemented for the analysis of data from Study EBO-301 (Protocol Version 5.0, dated 07 June 2023), entitled “A Phase 2/3, Randomized, Double-Blind, Placebo-controlled, Multicenter, Prospective Study to Assess the Efficacy, Safety, and Pharmacokinetics of Orally Administered Epetraborole in Patients with Treatment-refractory *Mycobacterium avium* Complex Lung Disease (MACrO₂),” which was intended as a single study to support registration. EBO-301 was designed as a seamless trial randomizing patients to either treatment with epetraborole plus an optimized background regimen (OBR) or placebo plus an OBR, with no pause between Phase 2 and Phase 3 enrollment. Phase 2 enrollment was completed in September 2023 (n=80), at which time enrollment in the Phase 3 part of the trial started immediately.

On 08 August 2024, the Sponsor terminated the trial based on topline, unblinded results from the Phase 2 part of the study and notified the Agency accordingly. The Phase 2 study met its primary objective of demonstrating the ability to validate the MACrO₂ PRO and showed a preliminary efficacy signal favoring epetraborole based on a responder analysis (39.5% [15/38] epetraborole vs 25% [10/40] placebo, p=0.19). However, the epetraborole plus OBR arm was not superior to the placebo plus OBR arm in sputum culture conversion rate. Nonetheless, the Sponsor is continuing with an analysis of the Phase 3 study data because of the positive Phase 2 clinical efficacy data noted.

This SAP supports the planned analyses of the primary, secondary, and exploratory efficacy and safety endpoints identified for evaluation both in the United States (US) by the Food and Drug Administration (FDA) as well as for other regulatory agencies outside the US. In accordance with the above protocol, any primary or secondary objectives or endpoints and hierarchical testing procedures that differ between regions will be specifically designated by “in the US” for FDA regulatory interpretation or “outside the US” for other regulatory agency interpretation in this document.

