2.2.7 Sample Size Determination and Power

Phase 2: The Phase 2 sample size (n=80) is based on the planned psychometric evaluation of the MACrO₂ PRO and is a sample size which may indicate an initial efficacy signal from this part of the study. When evaluating the individual items of the MACrO₂ PRO (not a scale with a total score), analyses will be within-patient, and this blinded evaluation will include all patients from both treatment groups. As a result, sample size requirements are not as high as in studies evaluating measures with composite scores. Basing

assumptions on convergent correlations with 90% power, an alpha of 0.05, and expected $R=0.4$, the minimum sample size needed is 61; therefore, a total Phase 2 sample size of 80 patients will be appropriate (polychoric correlations will be assessed given the MACrO₂ PRO uses rating scales with five response options). In addition, using assumed true response rates of 30% for the epetraborole arm and 10% for the placebo arm for a PRO symptom-based clinical response (in the US) or a microbiological culture conversion response (outside the US), a Phase 2 evaluation in approximately 40 patients per arm would have 85% power to show a significant treatment effect using a 2-sided alpha of 0.2. Therefore, this sample size is considered sufficient to provide the potential to show a preliminary efficacy signal.

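### The Phase 2 power of 85% assumes that all 40 randomised patients per arm enter Micro-ITT; under the 20% exclusion allowed for in Phase 3 it would be about 77%

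*Protocol*

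**What the plan says.** **Phase 2 power.** Protocol Section 8.2.4.1 states that "a Phase 2 evaluation in 40 patients per arm would have 85% power to show a significant treatment effect", "using assumed true response rates of 30% for the epetraborole arm and 10% for the placebo arm" and "using a 2-sided alpha of 0.2". SAP Section 2.2.7 gives the same statement: "a Phase 2 evaluation in approximately 40 patients per arm would have 85% power to show a significant treatment effect".

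**Who the 40 are.** Protocol Section 3.1.2: "The Phase 2 part of the study will consist of approximately 80 randomized patients (40 patients in the epetraborole + OBR group and 40 patients". The number in the power statement is therefore the full randomised number.

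**Who is analysed.** Protocol Section 8.1 says of the Micro-ITT Population: "Primary efficacy endpoint analyses in both Phase 2 and Phase 3 parts of the study will be performed in this patient population". SAP Section 3.2.3 agrees. Membership needs a MAC-positive culture both before the study and at Screening.

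**Phase 3 sizing.** Protocol Section 8.2.4.2 raises the total from 186 to 234 "to allow for approximately 20% of randomized patients to be excluded from the Micro-ITT Population", because some patients will lack a qualifying baseline culture.

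**Phase 2 as reported.** SAP Section 1 gives the responder result as "39.5% [15/38] epetraborole vs 25% [10/40] placebo, p=0.19", without naming the analysis population.

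**The concern.** The stated power refers to randomised patients, while the test it describes is run in a subset of them. The sponsor expected that subset to be materially smaller in Phase 3, and nothing in the documents makes the loss specific to Phase 3:

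- Protocol Section 4 applies one set of eligibility criteria to both phases.
- Section 8.1 gives one Micro-ITT definition.
- Section 7.5.3.2 lets some patients be randomised while the Screening culture is pending, and that culture may later prove negative. It makes no distinction by phase.

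At stake is how the Phase 2 comparison is read. SAP Section 1 says the trial was terminated on topline unblinded Phase 2 results, and that culture conversion was not superior on epetraborole. A reader weighing that result will look at the planned power, which should refer to the population analysed.

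**Working it through.** **Inputs.** Rates of 30% and 10%, 40 per arm, two-sided alpha 0.2 (Protocol 8.2.4.1). Test: Miettinen and Nurminen (Protocol 8.2.1.1). Exclusion allowance of about 20%, stated for Phase 3 only (Protocol 8.2.4.2). Reported denominators 38 and 40 (SAP Section 1).

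**Method.** For observed proportions a and b in arms of n1 and n2, with N = n1 + n2 and pooled proportion p, the statistic for zero difference is

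z = (a − b) / √[ p(1 − p)(1/n1 + 1/n2) × N/(N − 1) ].

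Reject when |z| ≥ 1.2816. Power is the sum of the products of the two binomial probabilities, at 0.30 and 0.10, over all outcomes that reject. The test is taken without stratification.

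**Step 1: reproduce the plan's figure at 40 per arm.** Exact enumeration gives 84.9%, which is the printed 85%. The pooled-variance normal approximation is close:

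- Φ[(0.20 − 1.2816 × √(0.32/40)) / √(0.30/40)] = Φ[(0.20 − 0.1146)/0.0866] = Φ(0.986) = 83.8%.

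The unpooled approximation gives 84.8% and the arcsine 84.7%. Fisher's exact test gives 77.8%, so it is not the source of the figure. The 85% therefore matches the planned test with every randomised patient analysed.

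**Step 2: confirm that Phase 3 carries the allowance.** 234 × 0.8 = 187.2, against the 186 planned for analysis. In the other direction, 186/0.8 = 232.5. Power at 124 and 62 is 89.7% (pooled approximation), which agrees with the stated 90% or so.

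**Step 3: apply the same allowance to Phase 2.** 40 × 0.8 = 32 per arm.

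- Exact Miettinen-Nurminen: 77.3%.
- Pooled approximation: Φ[(0.20 − 1.2816 × √(0.32/32)) / √(0.30/32)] = Φ[(0.20 − 0.1282)/0.0968] = Φ(0.742) = 77.1%.
- Unpooled 78.4%, arcsine 78.3%.

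**Step 4: range, because the documents give no exclusion rate for Phase 2.**

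| Excluded | Analysed per arm | Exact power |
|---|---|---|
| 0% | 40 | 84.9% |
| 5% | 38 | 83.2% |
| 10% | 36 | 81.5% |
| 15% | 34 | 79.5% |
| 20% | 32 | 77.3% |
| 25% | 30 | 75.0% |

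**Step 5: the reported denominators.** 38 + 40 = 78 of 80 randomised, so 2/80 = 2.5% are absent. Exact power at 38 and 40 is about 83%.

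**The case against.** The strongest reply is that the arithmetic is right. The sentence is conditional on 40 patients per arm, and at 40 per arm it is true. The 20% appears only in the Phase 3 paragraph, and carrying it to Phase 2 is an inference. This stands, and it makes the 77% conditional. It does not remove the point, because no section exempts Phase 2 from the loss or says that the 85% assumes none.

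The size of 80 was also not chosen for this power. Protocol Section 8.2.4.1 bases it on the psychometric evaluation, with a minimum of 61. That evaluation uses the FAS-PRO set rather than Micro-ITT, and even a 20% loss would leave 80 × 0.8 = 64. The efficacy power is an added remark at alpha 0.2 about a possible early signal, and the documents tie no go/no-go rule to it. This stands in full and limits the consequence.

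Three stronger readings are tempting, and the documents do not support them:

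- *The two paragraphs use contradictory exclusion rates.* The Phase 2 paragraph states no rate. A stated 20% beside an unstated zero is an omission, not a contradiction.
- *The reported 38 and 40 show that one of the planning figures was wrong.* A later denominator cannot show that a prospective allowance was a mistake, and SAP Section 1 does not say which population those patients form.
- *The chance of missing a true 30% versus 10% effect was 23%.* That is 1 − 0.773 and holds only if 20% were excluded. At 38 and 40 it would be about 17% (1 − 0.83), against the 15% implied by the plan.

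Finally, Phase 2 is complete, and SAP Section 1 limits changes after Version 2.0 to Phase 3. That affects where the correction goes, not whether the statement needs one.

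**Conclusion.** The point holds as an unstated assumption. The 85% is correct only if every randomised Phase 2 patient enters Micro-ITT. Under the allowance the sponsor used for Phase 3, power would be about 77%, some 7.6 points lower (84.9 − 77.3). At the denominators in SAP Section 1 it would be about 83%, less than 2 points below the exact figure at 40 per arm.

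These figures rest on the planned rates of 30% and 10%, two-sided alpha 0.2 and an unstratified Miettinen-Nurminen test. The 77% also assumes that the Phase 3 exclusion rate carries over to Phase 2. Shared eligibility, a shared Micro-ITT definition and the shared pending-culture route make that reasonable, but the documents do not state it. The 83% is informative about Micro-ITT only if the 38 and 40 are that population.

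The importance is minor. The sample size is not shown to be inadequate for its main purpose, and no prespecified decision depends on the difference.

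**What to change.** In Protocol Section 8.2.4.1 and SAP Section 2.2.7, or in the clinical study report now that Phase 2 is complete, do one of the following:

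- restate the Phase 2 power on the expected Micro-ITT numbers, which is about 77% at 32 per arm under the 20% allowance; or
- keep 85%, state that it assumes no exclusions from Micro-ITT, and explain why the allowance differs from Phase 3.

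In SAP Section 1, name the population behind the 38 and 40.

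The cost is wording only. The sample size of 80 stays, and no new data or analysis is needed. The printed power becomes somewhat less favourable under the first option.
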